### 9.3.5 Other safety information of interest

We will also collect information on the following situations, whether they are associated with an AE or not:

- Abuse or misuse.

## CONFIDENTIAL

- Occupational exposure (to a person other than the patient, for example spilling of IMP on hands of nurse or splashing in the eye).

Any occurrences of these should be reported in the same manner as SAEs (Section 9.4).

### 9.4 Reporting of SAEs to the Sponsor Pharmacovigilance Department

All SAEs, regardless of causality, must be reported to the Pharmacovigilance Department in an expedited manner.

SAEs should be documented on an SAE report form, using the completion guidelines provided.

**The SAE report form should be e-mailed to Pharmacovigilance Department within 24 hours of site staff becoming aware of the SAE.**

Each episode of an SAE must be recorded on a separate SAE report form. The NCI CTCAE Version 4.02 and protocol specific grading system for injection site reactions, must be used to grade the severity of each SAE, and the worst grade recorded. If new or amended information on a previously reported SAE becomes available, the Investigator should report this to the Pharmacovigilance Department on a new SAE report form.

If the SAE has not been reported within the specified timeframes, a reason for lateness must be added to the email when sending the SAE report form to the Pharmacovigilance Department.

Should the Investigator become aware of any AST-VAC2-related SAEs after the patient has withdrawn from the trial, these must also be reported to the PV Department within the specified timelines specified above.

#### 9.4.1 Events exempt from being reported as SAEs to the Pharmacovigilance Department

Events specified in this section do not require reporting as SAEs in this trial, unless hospitalisation is prolonged for any reason and then an SAE form must be completed. The events must still be recorded in the appropriate section of the eCRF.

**Elective admissions** – Elective admissions to hospital for procedures which were planned prior to entering the trial are not SAEs. Hospitalisation for administration of the IMP according to the trial protocol is also exempt from being reported as an SAE.

**Prolongation of hospitalisation** - Prolongation of hospitalisation without an associated adverse event (for example, prolonged hospitalisation while appropriate social care is set up for elderly patients).

**Death due to disease progression**- Cases of death due to disease progression do not require SAE reporting, unless considered related to the IMP.

### 9.5 Recording of adverse events and serious adverse events in eCRFs

All AEs, including SAEs, must be recorded in the eCRF for eligible patients. All concomitant medications, including herbal medications and supplements must be recorded. Any therapy used to treat the event must be recorded. The eCRF will be reconciled with the safety database during and at the end of the trial. Therefore, the sites should ensure the data entered on the SAE report form and the data entered into the eCRF are consistent. The Sponsor's Medical Advisor and the Investigator(s) will regularly review the safety data from both the safety and the clinical database.

## 9.6 Urgent safety measures

The Sponsor or Investigator may take appropriate urgent safety measures (USMs) in order to protect the patient of a clinical trial against any immediate hazard to their health or safety. This includes procedures taken to protect patients from pandemics or infections that pose serious risk to human health.

USMs may be taken without prior authorisation from the competent authority.

The Medicines and Healthcare products Regulations Agency (MHRA) and the Research Ethics Committee (REC) must be notified within three days of such measures being taken.

Should the site initiate a USM, the Investigator must inform the Sponsor immediately either by:

The notification must include:

- the date of the USM;
- who took the decision; and
- why action was taken.

The Sponsor will then notify the MHRA and the REC within three days of USM initiation.

## 9.7 Pregnancy

Female patients who become pregnant during the trial treatment period must be withdrawn from trial treatment immediately.

The Investigator must make every effort to try and ensure that a clinical trial patient or a partner of a clinical trial patient does not become pregnant during the trial or for six months afterwards. This should be done as part of the consent process by explaining clearly to the patient the potential dangers of becoming pregnant and also providing each patient with information about appropriate medically approved contraception. Two forms of medically approved contraception should be used, such as:

- oral contraceptives and condom; (oral, injected or implanted hormonal contraceptives should be used for four weeks before the patient joins the trial)
- intra-uterine device (IUD) and condom;
- diaphragms with spermicidal gel and condom.

Contraception should be effective before the patient is enrolled on the trial, throughout the trial and for six months after completing the trial.

Alternatively the patient may agree to sexual abstinence, effective from the first administration of IMP, throughout the trial and for *six* months afterwards. Abstinence is only considered to be an acceptable method of contraception when this is in line with the preferred and usual lifestyle of the subject. Periodic abstinence (e.g., calendar, ovulation, symptothermal, post-ovulation methods) and withdrawal are not acceptable methods of contraception.

It should be explained to the patient that if his partner is pregnant or breast-feeding when he is enrolled on the trial, the patient should use barrier method contraception (condom plus spermicidal gel) to prevent the unborn baby or the baby being exposed to AST-VAC2.

However, if a patient or a partner of a patient does become pregnant, the reporting procedures below must be followed.

Any pregnancy occurring in a patient or a patient's partner during treatment with an IMP or occurring within six months of last IMP administration must be reported to the Pharmacovigilance Department within 24 hours of the site staff becoming aware of it using a Pregnancy Report Form (provided in the ITF). It is the Investigator's responsibility to obtain consent for follow-up from the patient or patient's

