### 7.1.3 Evaluations within 7 days of study enrolment

The following must be performed **within 7 days before** study enrolment:

- Female patients able to have children must have a negative result on a human chorionic gonadotropin (HCG) pregnancy test (serum or urine test is acceptable).
- Complete physical examination;
- Height, weight, WHO PS,
- Vital signs (temperature, seated BP and pulse rate);
- ECG;
- Laboratory tests (blood/urine samples). Laboratory tests relating to specific eligibility criteria must be performed to confirm a patient's eligibility prior to study enrolment:
  - Haematology – haemoglobin (Hb), white blood cells (WBC) with differential count (neutrophils, lymphocytes, platelets and eosinophils).
  - Biochemistry – sodium, potassium, adjusted calcium, phosphate, urea, creatinine, total protein, albumin, bilirubin, alkaline phosphatase (ALP) and alanine aminotransferase (ALT) or aspartate aminotransferase (AST) and C-reactive protein (CRP).
  - CEA sample
  - Urinalysis – pH, glucose, protein and blood.
  - Baseline research bloods (Please see [Section 8.0](#))

Investigators must enrol the patient on the trial once confirmed as eligible (see [Section 4.2](#)) and prior to the patient's first AST-VAC2 vaccination.

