## 7.2 Evaluations during the trial

### Day of vaccination

- Symptom-directed physical examination: if clinically indicated, a symptom-directed physical examination is to be performed on the day of each vaccination before AST-VAC2 administration.
- WHO PS on the day of each vaccination.
- Vital signs, temperature, seated BP, pulse rate: must be assessed within 15 mins before the vaccination and within 15 mins after the vaccination.
- Adverse events and concomitant medications: At each visit, before each AST-VAC2 vaccination, an assessment of any AE experienced since the previous visit must be made by the Investigator, Research Nurse or suitably qualified member of the Investigator's team.

The start and stop dates of the AE together with the relationship of the event to AST-VAC2 must be recorded in the medical records.

All AEs must be graded according to NCI CTCAE Version 4.02 and protocol specific ISR grading system (See [Section 9.0](#) for further details regarding AE reporting requirements and ISR grading system).

Any concomitant treatment must be recorded in the medical records. (See [Section 9.0](#) for further details regarding AE reporting requirements.)

- COVID-19 vaccines: If a patient is administered a COVID-19 vaccination during the AST-VAC2 vaccination period, there should be an interval of 48 hours between the administration of the vaccines and they should be administered to different sites. The COVID-19 vaccine should be documented in the eCRF as a concomitant medication and any AEs should be assessed for causality to AST-VAC2 and the COVID-19 vaccination.
- Laboratory tests:  
Haematology and biochemistry:

**Week 1 vaccination**: laboratory tests must be repeated and reported prior to the first vaccination if the results used for enrolment purposes are >7 days prior to the day of vaccination.

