#### 7.3.2 End of Vaccination visit

The End of Vaccination visit should be performed 30 days (+/- 5 days) after the last AST-VAC2 vaccination. The following investigations should be performed wherever possible.

- A symptom-directed physical examination including WHO PS, vital signs (temperature, seated BP and pulse rate), weight
- Haematology: detailed in [Section 7.1.3](#).
- Biochemistry: detailed in [Section 7.1.3](#).
- CEA sample
- Urinalysis: detailed in [Section 7.1.3](#).
- ECG (unless otherwise indicated by the patient's condition)
- Assessment of AEs (all AEs should be collected until this visit; after this visit only information on ongoing and new AST-VAC2-related AEs should be collected; see [Section 9.3](#)) and
- Review of concomitant medications

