## CONFIDENTIAL

- Female patients able to have children must have a human chorionic gonadotropin (HCG) pregnancy test (serum or urine test is acceptable).
- Radiological assessment of disease: This must be repeated at the end of the vaccination schedule. Tumour measurements must be documented according to Immune-Related Response Criteria (irRC). (Refer to [Section 10.0](#)). Thereafter, assessment of disease to be performed as per standard clinical practice.

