**CONFIDENTIAL**

**7.5 Schedule of events**

Observation/Investigation	Pre-screening & trial screening	Within 7 days before study enrolment	During the trial			Two weeks post last vaccination	End of Vaccination visit 30 days after last vaccination	Research bloods: Up to 12 months post first vaccination g  Survival follow up: Up to 2 years post first vaccination f	Extended follow up: >2to 5 years post first vaccination (visits conducted by telephone)
			Vaccination at Weeks 1, 2, 3, 4, 5 and 6						
	Day -28 to -1 prior to first vaccination		Day -1 or Day of vaccination	Pre AST-VAC2 Within 15min prior	Post AST-VAC2 15 mins				
Written informed consent – HLA typing a	X								
Written informed consent– Main Trial b	X								
Adverse event evaluation l	From date of informed consent, throughout trial & monthly follow up thereafter until resolution j Ongoing drug-related AEs will be followed up until completion of extended follow up.								X n
Medical history	X								
Concomitant treatments	Throughout trial								X n
Radiological disease assessment k	X						X		
Pregnancy test (if applicable)		X					X		
Physical examination		X	X m				X		
Vital signs c		X		X	X		X		
WHO Performance Status d		X	X				X		
Demographics	X								
Height		X							
Weight		X					X		
Haematology, biochemistry, CEA		X	X e				X		
Urinalysis		X	X e				X		
Electrocardiogram		X					X		
AST-VAC2 administration	2 x id injections on each vaccination day, administered weekly, 7 days apart (+/- 1 day)								
Research bloods		X	Weeks 3, 4 and 6 pre-vaccination			X		3, 6 and 12 months post first vaccination	
Survival follow up l								X	

a) Patients will be asked to give written consent for HLA testing before any other further trial screening is performed. Thereafter, consent will be sought for the main trial.

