## CONFIDENTIAL

It is acceptable that the HLA testing is performed outside of the 28 day window: important to note that this test will be performed by a central laboratory therefore sites should plan accordingly to ensure that following consent, the sample is taken and shipped to ensure timely reporting in preparation for the proposed first vaccination.

- b) HLA A\*02:01 positive patients will be asked consider consenting to the main trial for trial treatment and enter the screening period.
- c) Vitals to include temperature, seated BP, pulse rate.
- d) WHO PS to be assessed on day of vaccination as well as during screening.
- e) Haematology, biochemistry, CEA and urinalysis: Week 1 vaccination: laboratory tests must be repeated and reported prior to the first vaccination if the results used for enrolment purposes are >7 days prior to the day of vaccination. Thereafter laboratory parameters are to be measured on Day-1 or Day of vaccination. Haematology and biochemistry results do not need to be reported and checked before each vaccination is given.
- f) Follow up for overall survival to be captured for two years post the first vaccination.  
For extended follow up details, see [Section 12.0](#).
- g) Research blood sampling required, pre, during and post treatment – Please see [Section 8.0](#).  
[REDACTED]
- [REDACTED]
- j) Monthly follow-up required ONLY for those AEs and SAEs considered drug-related (highly probable, probable or possible) that are present at time that patient completes the End of Vaccination visit. Monthly follow-up to continue until resolution, to baseline, stabilisation or patient starts another anti-cancer treatment.  
AE evaluation also to be performed as per [Section 7.4](#).
- k) Radiological disease assessment prior to trial start may have been taken prior to informed consent as part of routine diagnostic procedures. Tumour measurements must be reported according to Immune Response Related Criteria (irRC).
- l) AE evaluation according to CTCAE v4.02 and protocol specific grading system for ISR.
- m) Symptom directed physical examination only.
- n) During extended follow up, new and ongoing AST-VAC2 related AEs should be reported and only concomitant medications relevant to these AST-VAC2 related AEs should be recorded.

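### No pregnancy test is scheduled between the one before enrolment and the one 30 days after the last dose, so all six doses fall between tests; criterion 4 also starts contraceptive cover later than section 9.7 does

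*Protocol*

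**What the plan says.** **Testing.** Protocol 7.1.3, for the 7 days before enrolment: "Female patients able to have children must have a negative result on a human chorionic gonadotropin (HCG) pregnancy test". The only other HCG test is in 7.3.2, where "The End of Vaccination visit should be performed 30 days (+/- 5 days) after the last AST-VAC2 vaccination". The pregnancy row of the Schedule of Events (7.5) agrees: one mark in the pre-enrolment column, one in the End of Vaccination column, none under the vaccination columns. The day-of-vaccination list (7.2) and the two-week visit (7.3.1) name no pregnancy test in their legible text.

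**Stale results.** Section 7.2, under its haematology and biochemistry item, says "laboratory tests must be repeated and reported prior to the first vaccination if the results used for enrolment purposes are >7 days prior", counting back from dosing. Footnote e to the Schedule of Events gives the scope: "Haematology, biochemistry, CEA and urinalysis: Week 1 vaccination: laboratory tests must be repeated and reported prior to the first vaccination", on the same 7-day condition. HCG is not named, and 7.1.3 lists it apart from the laboratory tests.

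**Action on pregnancy.** Section 9.7: "Female patients who become pregnant during the trial treatment period must be withdrawn from trial treatment immediately". Section 9.2.2 puts pregnancy exposure on the reporting timelines of a serious adverse event.

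**Start of cover.** Section 9.7 wants contraception working before enrolment, with hormonal methods used for four weeks before the patient joins. Its abstinence alternative begins only at the first administration. Exclusion criterion 4 (4.1.2) also begins cover at the first administration and has no lead-in.

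**The concern.** The protocol treats pregnancy during treatment as a reason to stop at once, but schedules no test that could reveal one while doses are being given. The pre-treatment test is tied to enrolment rather than to dose 1, and no maximum time between the two is stated. The protocol accepts that blood and urine results go out of date after 7 days, but does not apply this to HCG.

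Eligibility and section 9.7 also set different starting points for cover. A site working from criterion 4, the text that decides eligibility, can enrol a patient who does not meet 9.7.

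At stake is foetal exposure to a first-in-human cell product. A pregnancy too recent for the enrolment test to detect, or begun between that test and dose 1, meets no further scheduled test until the course is over.

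**Working it through.** The plan gives no figure of its own here, so the check is a day count. Take dose 1 as day 0.

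**Inputs.** Six doses, 7 days (+/- 1) apart (5.2). End of Vaccination visit 30 days (+/- 5) after the last dose (7.3.2). First test 0 to 7 days before enrolment (7.1.3).

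**Current gap.**
- Doses on days 0, 7, 14, 21, 28 and 35.
- Second test: 35 + 30 = day 65. With the windows: 5 x 6 + 25 = 55 to 5 x 8 + 35 = 75.
- Test to test, enrolment on day 0: 65 + 0 = 65 to 65 + 7 = 72 days. With the windows, the 72-day case runs from 55 + 7 = 62 to 75 + 7 = 82.
- Enrolment d days before dose 1 adds d days. As an illustration, a first test on Day -28 (an assumption taken from the screening window) gives 65 + 28 = 93 days.
- One two-week dose delay (5.3.2) adds 14 days.
- Doses between the two tests: 6 of 6 in every case where the course is completed.

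**With tests added before vaccinations 1 and 4 (days 0 and 21).** Assume HCG turns positive L days after conception, with L = 7 or 14; the documents give no lag. Let c be the day of conception. The table covers pregnancies not found by the pre-enrolment test.

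| Conception | Found when | Doses received while pregnant | Now |
|---|---|---|---|
| c at or before -L (-7 or -14) | day 0 | 0 | 6 |
| c after -L, up to day 0 | day 21, since c + L is at most 14 | 3 (days 0, 7, 14) | 6 |
| c after day 0, up to 21 - L (day 14 or 7) | day 21 | doses on days 21, 28 and 35 avoided | not avoided |
| c later than 21 - L | End of Vaccination | unchanged | unchanged |

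An example of the last row: conception on day 8 with L = 14 still receives the doses on days 14, 21, 28 and 35, as now. The longest planned interval without a test after dose 1 falls from 65 days to 65 - 21 = 44.

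**Start of cover, side by side.**

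| | Contraception | Hormonal lead-in | Abstinence |
|---|---|---|---|
| Section 9.7 | before enrolment | four weeks | from dose 1 |
| Criterion 4 | from dose 1 | none | from dose 1 |

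The timing phrase in criterion 4 could be attached to abstinence alone. On that reading the criterion sets no start for contraception at all and still has no lead-in, so it does not enforce 9.7 either way.

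**The case against.** The strongest reply is that the withdrawal rule does not depend on a scheduled test. Section 9.7 requires that patients be told at the outset why pregnancies must be reported. Adverse events are reviewed before every vaccination (7.2), with an examination if symptoms call for one, and nothing bars an unscheduled HCG test. This stands. A reader might infer that a pregnancy could not be detected during dosing, or that the rule cannot operate. The documents support only the narrower statement that it has no scheduled trigger.

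A reader might also infer that all cover begins only at dose 1. Section 9.7 says otherwise for contraception, and it accepts abstinence only where this is already the patient's settled way of life, which lowers the practical risk. What remains is a conflict between two sections, plus a late formal start for abstinence.

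A third inference would be that male patients need the same change. The documents do not support it: a man has no exposure to the product before dose 1, so starting his cover then is coherent.

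Test frequency is a risk judgement. The non-clinical sections that would inform it are redacted, and no visible text sets a frequency that the schedule breaches. The visible text in 3.3.1 describes irradiated, terminally differentiated cells that are not expected to proliferate. This limits the testing point to an inexpensive improvement, but does not touch the criterion 4 conflict. Redaction is unlikely to hide a further test, since the pregnancy row of the Schedule of Events is legible.

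**Conclusion.** The point holds in two parts.

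- **Testing gap (an inexpensive safety improvement).** Two tests are scheduled, with all six doses between them. That needs no assumption beyond a completed course. The 65 to 72 days assume the planned schedule with enrolment on the day of dose 1.
- **Start of cover (wrong as written).** Criterion 4 and section 9.7 do not agree, and criterion 4 governs entry.

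The reduction from 6 doses to 0 or 3 rests on the assumed 7 to 14 day lag and applies only to pregnancies begun before dose 1. Conceptions within that lag of the vaccination 4 test, or after it, would still be found by schedule only at the End of Vaccination visit.

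The practical size is small. The trial recruits up to eight patients, the documents do not say how many could become pregnant, and two contraceptive methods or habitual abstinence are required. This is a matter of patient and foetal safety only; no endpoint, population or analysis is affected.

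**What to change.** 1. In 7.2 and the Schedule of Events, for female patients able to have children, add a urine or serum HCG test on Day -1 or the day of vaccinations 1 and 4, with a negative result read before the dose is given. Footnote e already uses this window for laboratory tests: "Thereafter laboratory parameters are to be measured on Day-1 or Day of vaccination".
2. Bring criterion 4 into line with 9.7: contraception effective before enrolment, and four weeks of prior use for hormonal methods. In both places, start abstinence for female patients no later than the pre-enrolment pregnancy test. Leave criterion 5 (male patients) as it is.

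**Cost.** Two HCG tests per applicable patient, at visits already planned. Urine is already collected at vaccination 4. At vaccination 1 an extra sample may be needed when enrolment results are 7 days old or less. The hormonal lead-in adds no new requirement, because 9.7 already asks for it. The change needs a protocol amendment, which may go to REC, HRA and MHRA review (14.1), revised consent text, and re-consent where 14.8 applies. It helps only patients not yet dosed or still being dosed; the documents do not state recruitment status.

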## CONFIDENTIAL

partner. In addition, the Investigator must be made aware of the need to obtain contact details for the patient's partner's GP. The Pharmacovigilance Department will follow-up all pregnancies for the pregnancy outcome via the Investigator, using a Pregnancy Report Form.

The Investigator should document within the patient notes, that the patient confirms consent for the Sponsor to collect pregnancy follow-up information. In the case that the partner of a patient becomes pregnant, a consent form should be provided to the patient's partner in order to obtain consent for collecting privacy data, in accordance with the data protection act.

The Investigator must ensure that all patients are aware at the start of a clinical trial of the importance of reporting all pregnancies (in themselves and their partners) that occur whilst being treated with the IMP and occurring up to six months after the last IMP administration. The Investigator should offer counselling to the patient and/or the partner, and discuss the risks of continuing with the pregnancy and the possible effects on the foetus. Monitoring of the patient should continue until the conclusion of the pregnancy, if the patient or patient's partner has consented to this. Monitoring of the baby should continue until 12 months after birth, if the patient or patient's partner has consented to this.

